2.15.2 Key secondary endpoint: ORR in cohort B

One interim analysis is planned for cohort B based on approximately the first [REDACTED] participants. Evaluable participants are defined as enrolled participants who have been followed for at least two tumor assessments or have discontinued the study earlier. The primary intent of the interim analysis is to stop the cohort early for lack of efficacy (futility).

The decision whether to continue or stop enrollment and/or treatment will be based on the PPoS.

$$\text{PPoS} = \text{Prob}[\text{Final observed ORR} \geq [REDACTED] | x, n]$$

A minimally informative Beta distribution prior (Neuenschwander et al 2008) with prior mean equal to 20% will be used, i.e., the prior distribution will be Beta (0.25, 1) for the PPoS calculations at the interim analysis.

The cohort will be stopped for futility at the interim analysis if the observed ORR is [REDACTED] corresponding to [REDACTED] or less responders (at least [REDACTED] responders out of [REDACTED] participants are required for the cohort to proceed). If the futility criterion is met, the predictive probability of observing a success in the future based on the existing data will be [REDACTED]

All evaluable participants in the cohort at the time of the data cut-off for the interim analysis will be used.

If futility is concluded, the enrollment of participants in the cohort will be stopped. The enrollment in cohort A will continue, if applicable.

Table 2-10 provides the PPoS at the primary analysis based on different numbers of responders observed at the interim analysis. For [REDACTED] or more responders, PPoS exceeds [REDACTED] and the cohort enrollment will continue after the interim analysis.

Table 2-11 PPoS at the final analysis based on various numbers of responders observed

Responders at IA out of [REDACTED] participants	Predictive probability of success (%)
1	[REDACTED]
2	[REDACTED]
3	[REDACTED]
4	[REDACTED]
5	[REDACTED]
6	[REDACTED]

3 Sample size calculation

A total of 120 participants will be enrolled in 2 separate cohorts that will recruit in parallel: 90 in cohort A and 30 in cohort B, if none of the cohorts is stopped for futility at the time of the corresponding interim analysis.

An additional group including all participants whose tumors harbor an STK11 mutation will be formed by pooling participants from cohorts A and B. Around 30 of these participants are anticipated in cohort B and another ~30 STK11 mutated participants are expected from cohort A based on the prevalence of STK11 mutation among patients with KRAS G12C-mutated advanced NSCLC in prior studies, hence the STK11 mutated group should have approximately 60 participants ([Ricciuti et al 2021](#)).

3.1 Primary endpoint(s)

The calculation of sample size and operating characteristics for the analysis of the primary endpoint, ORR estimate and confidence interval, are based on the model and assumptions in [Section 2.6](#).

The exact 95% CIs for various sample sizes and potential observed ORRs are shown in [Table 3-1](#).

Table 3-1 Exact binomial 95 percent confidence intervals for various sample sizes and observed ORRs (cohort A)

Sample size (N)	Number of responders	Observed ORR (%)	95% exact CI (%)
90	30	33.3	25.0 - 41.7

The operating characteristics (for 90 participants) are shown in [Table 3-2](#). The table presents the probability of stopping at the interim analysis, the probability for a positive conclusion (i.e., not stopped at IA for futility, and success criteria met at final analysis), and a negative conclusion (i.e., not stopped at IA for futility but success criteria not met at final analysis) under different underlying true ORR.

Table 3-2 Operating Characteristics (cohort A)

True ORR (%)	Prob. to stop at IA* (%)	Prob. of success at final analysis (%)	Prob. of failure at final analysis (%)
33.3	10.0	80.0	20.0

True ORR (%)	Prob. to stop at IA* (%)	Prob. of success at final analysis (%)	Prob. of failure at final analysis (%)
[REDACTED]	[REDACTED]	[REDACTED]	[REDACTED]

*Assuming IA at 30 evaluable participants

The operating characteristics at this sample size have around [REDACTED] probability of stopping the trial for futility when the true ORR is [REDACTED] or less. Also, when the true ORR is [REDACTED] the probability of a positive conclusion at the final analysis with 90 participants is around [REDACTED]. For a true ORR of [REDACTED] or higher, the probability of a positive conclusion at the final analysis is [REDACTED].

The calculations were made using the software R.

3.2 Secondary endpoint(s)

The calculation of sample size and operating characteristics for the analysis of the key secondary endpoint, cohort B ORR estimate and confidence interval, are based on the model and assumptions in [Section 2.7](#).

The exact 95% CIs for various sample sizes and observed ORRs are shown in [Table 3-3](#).

Table 3-3 Exact binomial 95 percent confidence intervals for various sample sizes and observed ORRs (cohort B)

Sample size (N)	Number of responders	Observed ORR (%)	95% exact CI (%)
[REDACTED]	[REDACTED]	[REDACTED]	[REDACTED]

The operating characteristics (for 30 participants) are shown in [Table 3-4](#). The table presents the probability of stopping at the interim analysis, the probability for a positive conclusion (i.e., not stopped at IA for futility and success criteria met at final analysis), and a negative conclusion (i.e., not stopped at IA for futility but success criteria not met at final analysis) under different underlying true ORR.

Table 3-4 Operating characteristics (cohort B)

True ORR	Prob. to stop at IA* (%)	Prob. of success at final analysis (%)	Prob. of failure at final analysis (%)
[REDACTED]	[REDACTED]	[REDACTED]	[REDACTED]

True ORR	Prob. to stop at IA* (%)	Prob. of success at final analysis (%)	Prob. of failure at final analysis (%)
[REDACTED]	[REDACTED]	[REDACTED]	[REDACTED]

The operating characteristics at this sample size have around [REDACTED] probability of stopping the trial for futility when the true ORR is [REDACTED] or less. Also, when the true ORR is [REDACTED], the probability of a positive conclusion at the final analysis with [REDACTED] participants is circa [REDACTED]. If the true ORR is [REDACTED] or higher, the probability of a positive conclusion at the final analysis is [REDACTED].

The calculations were made using the software R.

4 Appendix

4.1 Imputation rules

4.1.1 Study drug

Complete dates are required per eCRF. For exceptional cases where a missing or partial date remains after data cleaning, the following rules should be used for the imputation of the dose end date of the study treatment:

Scenario 1

If the dose end date is completely missing and there is no end of treatment (EOT) and no death date, the participant is considered as ongoing. The participant should be treated as ongoing, and the cut-off date should be used as the last dosing date.

Scenario 2

If the dose end date is completely or partially missing and the EOT page is available:

Case 1: The dose end date is completely missing and the EOT completion date is complete, then this latter date should be used.

Case 2: Only year (YYYY) of the dose end date is available and YYYY < the year of EOT date, then use 31DECYYYY.

Case 3: Only year (YYYY) of the dose end date is available and YYYY = the year of EOT date, then use EOT date.

Case 4: Both year (YYYY) and month (MMM) are available for dose end date and YYYY = the year of EOT date and MMM < the month of EOT date, then use last day of the Month (MMM).

Case 5: Both year (YYYY) and month (MMM) are available for dose end date and YYYY = the year of EOT date and MMM = the month of EOT date, then use EOT date.

All other cases should be considered as a data issue and the data manager of the study should be contacted.

After imputation, compare the imputed date with start date of treatment.

- If the imputed date is < start date of treatment, then use the treatment start date
- Otherwise, use the imputed date

Participants with missing start dates are to be considered missing for all study treatment related calculations and no imputation will be made. If the start date is missing, then the end-date should not be imputed.

4.1.2 AE, concomitant medication (CM), and safety assessment date imputation

Table 5-1 Imputation of start dates (AE, CM) and assessments (lab, ECG, vital signs)

Missing element	Rule
day, month, and year	No imputation will be done for completely missing dates
day, month	If available year = year of study treatment start date, then If stop date contains a full date and stop date is earlier than study treatment start date then set start date = 01JANYYYY, Else set start date = study treatment start date. If available year > year of study treatment start date, then 01JANYYYY. If available year < year of study treatment start date, then 01JULYYYY.
day	If available month and year = month and year of study treatment start date, then If stop date contains a full date and stop date is earlier than study treatment start date then set start date= 01MONYYYY, Else set start date = study treatment start date. If available month and year > month and year of study treatment start date, then 01MONYYYY. If available month and year < month year of study treatment start date, then 15MONYYYY.

Table 5-2 Imputation of end dates (AE, CM)

Missing element	Rule
day, month, and year	Completely missing end dates (incl. ongoing events) will be imputed by the end date of the on-treatment period*.
day, month	If a partial end date contains the year only, set end date = earliest of (31DECYYYY, end date of the on-treatment period*).
day	If a partial end date contains the month and year, set end date = earliest of (last day of the month, end date of the on-treatment period*).

*= last treatment date plus 30 days not > (death date, cut-off date, withdrawal of consent date)

Any AEs and ConMeds with partial/missing dates will be displayed as such in the data listings.

Any AEs and ConMeds which are continuing as per data cut-off will be shown as 'ongoing' rather than the end date provided.

4.1.3 Prior ANP, concomitant ANP, non-drug therapy, and diagnosis date imputation

Table 5-3 Imputation of end dates (prior ANP, concomitant ANP, non-drug therapy, diagnosis)

Missing date Scope	Missing element	Rule
Post-treatment anti-neoplastic therapy (including radiotherapy/medication/surgery) start date	Day, month	Imputed date = max (last date of study treatment + 1, 01JAN).
	Day	Imputed date=max (last date of study treatment + 1, first day of the month).
Post-treatment anti-neoplastic therapy (including radiotherapy/medication/surgery) end date	All scenarios	No imputation
Prior anti-neoplastic surgery start date	Day, month	If available year = year of treatment start date, then set start date = treatment start date, else set start date = 01JULYYYY.
	Day	If available month and year = month and year of treatment start date, then set start date = study treatment start date, else set start date = 15MONYYYY.
Prior anti-neoplastic surgery start date	All scenarios	No imputation
Prior anti-neoplastic therapy – medication, date of progression	Day	Set to max (start date of prior antineoplastic therapy, 1st day of the month), if day is missing
	Day, month	No imputation
Non-drug therapy start date	Day and month (same as CM)	If available year = year of study treatment start date, then if stop date contains a full date and stop date is earlier than study treatment start date, set start date = 01JANYYYY, else set start date = study treatment start date. If available year > year of study treatment start date, then set start date = 01JANYYYY. If available year < year of study treatment start date, then set start date = 01JULYYYY.
	Month	If available year = year of study treatment start date, then

Missing date Scope	Missing element	Rule
		if stop date contains a full date and stop date is earlier than study treatment start date, then set start date= DDJANYYYY, else set start date = study treatment start date.
		If available year > year of study treatment start date, then set start date = DDJANYYYY.
		If available year < year of study treatment start date, then set start date = DDJULYYYY.
	Day (same as CM)	If available month and year = month and year of study treatment start date, then If stop date contains a full date and stop date is earlier than study treatment start date, then set start date = 01MONYYYY, else set start date = study treatment start date.
		If available month and year > month and year of study treatment start date, then set start date = 01MONYYYY.
		If available month and year < month year of study treatment start date, then set start date = 15MONYYYY.
Date of Initial Diagnosis (of cancer), date of most recent recurrence*	Day and month	Set to 01JANYYYY.
	Day	Set to 01MONYYYY.

* If because of this imputation the chronology of the events is altered, then the imputation should be made to the minimum value up to where the chronology remains unchanged. E.g., if due to imputation the date of most recent recurrence becomes prior to the initial diagnosis date then it should be set to initial diagnosis date.

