10.8.4.5.3 Incomplete dates for last known date patient alive or death

All dates must be completed with day, month and year. If the day is missing, the 15th of the month will be used for incomplete death dates or dates of last contact.

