2.1.3.7 Baseline

For safety and efficacy evaluations, the last available assessment on or before the date of start of study treatment is defined as “baseline” assessment.

If labs with duplicate laboratory measurements taken at the last assessment date on or before the start date of study treatment, then the rule described below will be applied for the calculation of baseline.

If values are from central and local laboratories, the value from central assessment should be considered as baseline.

For gradable labs:

- The value of lower CTCAE grade will be considered as the baseline value.
- If several records have the same absolute grade, but in different directions, two baselines should be created, the record with grade below 0 should be the baseline of the 'Hypo' parameter, and the other record should be the baseline for the 'Hyper' parameters.

For non-gradable labs:

- If both within normal range: take average value
- If one within normal range and the other outside: take the one within normal range
- If both outside normal range: take the one closest to the normal range

If participants have no value as defined above, the baseline result will be missing.

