2.7.3 Handling of intercurrent events

ORR by BIRC for cohort B

The analysis will account for different intercurrent events as follows:

1. Treatment discontinuation for any reason: Tumor assessment data collected irrespective of treatment discontinuation will be included to derive BOR (treatment policy strategy).
2. Start of a new anti-neoplastic therapy: If any new anti-neoplastic therapy is initiated, responses documented after the use of new anti-neoplastic therapy will be considered as non-response (composite strategy). Protocol-allowed radiotherapy is exempted.

3. Any public health emergency as declared by local or regional authorities, i.e., pandemic, epidemic or natural disaster: tumor assessment data collected irrespective of such unforeseen events will be considered for the BOR (treatment policy strategy).

DOR by BIRC for cohort A and cohort B

The analysis will account for different intercurrent events as follows:

1. Treatment discontinuation for any reason: Tumor assessment data collected irrespective of treatment discontinuation will be included to derive DOR (treatment policy strategy).
2. Start of a new anti-neoplastic therapy: If any new anti-neoplastic therapy (with the exception of protocol-allowed radiotherapy) is initiated, progression or death occurring after the use of new anti-neoplastic therapy will not be considered and the DOR will be censored.
3. Any public health emergency as declared by local or regional authorities, i.e., pandemic, epidemic or natural disaster: tumor assessment data collected irrespective of such unforeseen events will be considered for the DOR (treatment policy strategy).

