2.8.1.4 Progression-free survival

Progression-free survival is defined as the time from the date of first dose of study treatment to the date of the first documented progression or death due to any cause. PFS will be evaluated based on Investigator or BIRC assessment according to RECIST 1.1.

PFS will be censored if no PFS event (radiological progression or death) is observed prior to the first to occur between: (i) the analysis cut-off date, and (ii) the date when a new anti-neoplastic therapy (with the exception of protocol-allowed radiotherapy) is started. The censoring date will be the date of the last adequate tumor assessment prior to cut-off/start of new anti-neoplastic therapy.

Clinical deterioration will not be considered as documented disease progression. A PFS event date will be included in the analysis if it occurs after one missing tumor assessment. If the PFS event is observed after two or more consecutive missing tumor assessments, PFS will be censored at the last adequate tumor assessment prior to the first missing assessment.

The date of last adequate tumor assessment is the date of the last tumor assessment with overall lesion response of CR, PR, SD, or non-CR/non-PD before an event or a censoring reason occurred. In this case the last tumor evaluation date at that assessment will be used. Participants without a post-baseline tumor assessment will be censored at the date of first dose of study treatment.

A missing adequate tumor assessment is defined as a tumor assessment (TA) not performed or a tumor assessment with overall lesion response of “not evaluable (NE)”. The rule to determine the number of missing TAs is based on the time interval between the date of last adequate tumor assessment and the date of an event. Details are described in [Section 4.5](#).

[Table 2-5](#) shows the censoring and event date options and the outcomes for PFS. Details about censoring rules for PFS follow the RECIST 1.1 guidelines ([\[Study Protocol Section 10.8\]](#)) and are provided in [Section 4.5](#).

The distribution of PFS will be estimated using the Kaplan-Meier method, and the Kaplan-Meier curve, median, and 95% CI of the median will be presented by cohort.

A subgroup analysis of PFS will be prepared for cohort A for the subgroups 4a to 4h.

Censoring pattern for PFS

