4.1.4 Other imputations

Incomplete assessment dates for tumor assessment

All investigation dates (e.g., MRI scan, CT scan) must be completed with day, month and year. If one or more assessment dates are incomplete but other investigation dates are available, the incomplete date(s) are not considered for calculation of the assessment date and assessment date is calculated as the latest of all investigation dates (e.g., MRI scan, CT-scan) if the overall lesion response at that assessment is CR/PR/SD/NE. Otherwise – if overall response is progression – the assessment date is calculated as the earliest date of all investigation dates at that evaluation. If all measurement dates have no day recorded, the 1st of the month is used. If the month is not completed, for any of the investigations, the respective assessment will be considered to be at the date which is exactly between the previous and the following assessment. If a previous and following assessment is not available, this assessment will not be used for any calculation.

Incomplete death date or last known participant alive date from survival eCRF page

For rare cases when either day is missing or both month and day are missing for the date of death, the following partial imputation rules will be implemented:

- If only day is missing, then impute the last known participant alive date (from “Survival” eCRF) or death date with max[(01MONYYYY), any valid date used for deriving last contact date + 1].
- If both day and month are missing, then impute the last known participant alive date or death date with max[01JANYYYY, any valid date used for deriving last contact date + 1].

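### In a limited set of partially dated records, two SAP imputation rules can make a post-dose result the baseline or turn a genuine progression into a DOR/PFS censoring

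*SAP*

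**What the plan says.** **Assessment dates.** Table 5-1 (SAP 4.1.2) covers AE and concomitant-medication start dates and, by its title, lab, ECG and vital-sign assessments. If the known month and year match first dose (or only the year is known and it matches), a record with a complete stop date before first dose goes to the start of that month or year. For every other such record the rule is "Else set start date = study treatment start date". A later known month goes to its 1st, an earlier one to its 15th. SAP 2.1.3.7 selects baseline purely by date: "the last available assessment on or before the date of start of study treatment is defined as" the baseline assessment.

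**New-therapy dates.** Table 5-3 (SAP 4.1.3) imputes a post-treatment anti-neoplastic start date with a missing day as "Imputed date=max (last date of study treatment + 1, first day of the month", and with day and month missing as "Imputed date = max (last date of study treatment + 1, 01JAN". Under SAP 2.7.3, "progression or death occurring after the use of new anti-neoplastic therapy will not be considered and the DOR will be censored". SAP 2.8.1.4 likewise censors PFS if no event occurs before the earlier of the cut-off and "the date when a new anti-neoplastic therapy (with the exception of protocol-allowed radiotherapy) is started". A footnote to Table 5-3 stops imputation from changing the order of events, but it is attached only to the initial-diagnosis and most-recent-recurrence dates.

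**Death dates.** With the day missing, SAP 4.1.4 takes the later of the 1st of the month and the day after last contact. With day and month missing, the instruction is to "impute the last known participant alive date or death date with max[01JANYYYY, any valid date used for deriving last contact date + 1". Protocol 10.8.4.5.3 says: "If the day is missing, the 15th of the month will be used for incomplete death dates or dates of last contact".

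**The concern.** A lab, ECG or vital-sign result has no stop date, so when its known month matches first dose it always takes the first-dose date. A C1D15 result can therefore pass as baseline. Change-from-baseline and shift tables would then compare later values with one already affected by treatment.

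For new therapy, the imputed date is the earliest one admissible after the last dose. A progression that fell between that date and the true therapy start is treated as having followed the therapy. It is then dropped, and the participant is censored at an earlier scan. Replacing events with censorings tends to lengthen DOR (a key secondary endpoint) and PFS, which is the favourable direction in a single-arm trial.

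The death rule uses the earliest admissible day where the protocol uses mid-month, so OS, and death events in PFS and DOR, are dated somewhat early.

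**Working it through.** The plan states no figure to reproduce. The rules were applied to each day of a 365-day year. The gaps between last dose, progression, new therapy and last contact are assumptions, shown as ranges, because the documents do not give them.

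**1. Result moved to the first-dose day.** A result taken k days after first dose shares its month if the start day plus k does not exceed the month length. The count is 365 − 12k.

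| k (days) | Matching start dates | Share |
|---|---|---|
| 14 (C1D15) | 365 − 168 = 197 | 54% |
| 11 (C1D15, window −3) | 365 − 132 = 233 | 64% |
| 17 (C1D15, window +3) | 365 − 204 = 161 | 44% |
| 21 (C2D1) | 365 − 252 = 113 | 31% |

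With day and month both missing, the year matches for 365 − 14 = 351 start dates (96%) at k = 14. In protocol Table 1-3, labs and ECGs have a C1D15 visit and vital signs do not; the first post-dose vital signs are at C2D1. The 54% therefore applies to labs and ECGs only.

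There may be no true Day-1 lab to compete with the moved one. Protocol 1.3 does not require hematology and chemistry to be repeated on C1D1 if they were done within the preceding 72 hours.

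**2. Progression placed after an imputed therapy date.** Let g be the true number of days from progression to new therapy.

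- *Last dose on or after the progression scan:* last dose + 1 falls after the scan, so 0% of progressions are lost.
- *Last dose 10 to 60 days before progression:* the progression is lost if it falls after the 1st of the therapy month (day missing) or after 1 January (day and month missing).

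| g (days) | Lost, day missing | Lost, day and month missing |
|---|---|---|
| 7 | 269/365 = 74% | 357/365 = 98% |
| 14 | 185/365 = 51% | 350/365 = 96% |
| 21 | 101/365 = 28% | 343/365 = 94% |
| 28 | 18/365 = 5% | 336/365 = 92% |

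Example: last dose 10 June, progression 10 July, therapy truly started 25 July but recorded as July. The imputed date is max(11 June, 1 July) = 1 July, so the progression is dropped. With last dose 15 July the imputed date is 16 July and the progression counts.

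Deaths are not exposed in this way. A death necessarily follows any therapy received, so dropping it is what the rule intends.

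**3. Death with the day missing.** The 1st of the month is early by the day of the month minus 1, on average 5,373/365 = 14.7 days (maximum 30). The 15th has a mean error of 14.7 − 14 = 0.7 day (range −14 to +16). With the SAP's last-contact floor and last contact 7, 14, 28 or 84 days before death, the mean shift is 5.3, 10.0, 14.6 or 14.7 days early.

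**The case against.** The strongest reply is that each rule is already bounded and the records are probably few.

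- **New therapy.** Protocol 6.1.4 and 8.4.1 foresee dosing until BIRC confirms progression, and the last-dose + 1 floor then protects the event completely. With only the day missing, the risk falls quickly as the gap to new therapy grows. This stands, but two groups remain outside the floor. Participants who stop for other reasons are still scanned, even after starting new therapy (protocol 7.1.2 and 8.4.1). Those interrupted at progression who never resume have a last non-zero dose before the scan (SAP 2.1.3.4). Protocol 7.1 lets information on new treatments be collected by telephone or email, so partial dates are plausible.
- **Baseline.** If a true Day-1 lab exists, SAP 2.1.3.7 prefers central over local values and then the lower CTCAE grade. The on-treatment period also includes the first-dose day, so a worse result moved there is not necessarily lost. This limits the damage for labs. It does not help where no Day-1 value exists, and 2.1.3.7 gives no tie rule for ECGs.
- **Death.** Protocol 10.8.4 describes itself as guidance, and 10.8.4.1 lets departures be defined in the analysis-plan documentation. SAP 4.1.4 calls these cases rare, and its floor prevents a death being dated before a known contact. Early dating shortens OS, which does not favour the drug. This largely stands, so the death rule is only a matter of reconciliation.

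The tested endpoint, ORR, is not put at risk by the therapy rule: responses after new therapy do not count, so the earliest-day date is conservative for BOR.

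**Conclusion.** The point holds for specific records. A lab, ECG or vital-sign result whose known month and year (or year) match first dose can wrongly become baseline. A progression that occurred after the last dose and before a partially dated new therapy can wrongly be censored in DOR and PFS. The percentages above are per-record probabilities under assumed gaps. The documents give no rate of partial dates, so the net effect on any endpoint cannot be stated.

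Three stronger readings are tempting, and the documents do not support them:

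- *Genuine progressions are censored as a rule.* They are not: anyone dosed through progression is unaffected.
- *All partial lab, ECG and vital-sign dates go to the first-dose day.* Table 5-1 does this only on a month/year or year match.
- *Median DOR shifts by a stated percentage.* Under an exponential model, losing one of an assumed six events raises the median by somewhat less than 6/5 − 1 = 20%. That presumes the loss has already happened, and the SAP plans Kaplan-Meier medians, which need not move in the same way.

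The death-date difference is minor: up to about 15 days early on average when only the day is missing, and less when last contact is recent.

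**What to change.** 1. **Table 5-1:** limit the first-dose-day rule to AE and concomitant-medication start dates. Exclude lab, ECG and vital-sign results with imputed dates from baseline selection unless they are known to be pre-dose.
2. **Table 5-3:** extend the footnote's chronology safeguard so that an imputed therapy date alone cannot remove a documented event from DOR or PFS. In practice this means progression; deaths after new therapy should be handled as now. Alternatively, keep the rule and pre-specify a sensitivity analysis that retains such progressions. Keep the earliest-day rule for BOR.
3. **SAP 4.1.4:** reconcile with protocol 10.8.4.5.3 when the day is missing, for example max(15MONYYYY, last contact + 1), or state why the SAP departs from it.

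The cost is SAP wording and minor programming before database lock. A few progressions that truly followed new therapy may be counted as events, which would slightly shorten DOR and PFS.
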